8.2.3 Visit 3 – 30-day Follow-up

One month (approximately 30 days \pm 7 days) after the ablation procedure, the patient will visit the study site and the following assessments will occur:

- Record all concomitant medications.
- All concomitant procedures.
- QOL questionnaires EORTC QLQ-C30 and the lung-specific QLQ-LC13. The questionnaires may be administered over the phone, as needed.
- Numeric Pain Rating Scale.
- Collect height and body weight for BMI, and evaluate ECOG performance status.
- CT scan to determine soft tissue lesion details (e.g., size, lesion type, location, shape). [REDACTED]
- Laboratory tests, as follows:
 - CBC (with differentials).
 - Coagulation tests (APTT, INR, PT, PTA, PTT).
- Technique efficacy, defined as ablation of the target lesion according to the protocol and covered completely, with an adequate margin, as defined by the performing physician (that is, the ablation zone completely overlaps or encompasses the target lesion plus an ablative margin). [REDACTED]
- Record readmission to any hospital for any reason within 30 days of the ablation. The Investigator will assess the reason for the admission and capture the reason in the clinical database.
- All AEs/SAEs.

8.2.4 Visit 4 – 6-month Follow-up

Visit 4 occurs 6 months (\pm 1 month) after the first ablation procedure (Visit 2A). The patient must visit the study site for the following assessments:

- Record all concomitant medications.
- All concomitant procedures.
- QOL questionnaires EORTC QLQ-C30 and the lung-specific QLQ-LC13. The questionnaires may be administered over the phone, as needed.

- Collect height and body weight for BMI, and evaluate ECOG performance status.
- CT scan to determine soft tissue lesion details (e.g., size, lesion type, location, shape). [REDACTED]
- Obtain PFTs (spirometry, diffusion capacity (DLCO), lung volume tests, 6-minute walk or pulse oximetry, and FeNO tests).
- Laboratory tests, as follows:
 - a. Complete blood count (CBC; with differentials).
 - b. Coagulation tests (APTT, INR, PT, PTA, PTT).
- Record the number of successful repeat ablations, if applicable.
- All AEs/SAEs.

8.2.5 Visit 5 – 12-month Follow-up / End-of-Study

Approximately 12 months (\pm 1 month) after the first ablation procedure is Visit 5, the end-of-study visit. At this final visit of the study, the patient will visit the study site where the following assessments will occur:

- Record all concomitant medications.
- All concomitant procedures.
- QOL questionnaire (EORTC QLQ-C30) and the lung-specific QLQ-LC13. The questionnaires may be administered over the phone, as needed.
- Collect height and body weight for BMI, and evaluate ECOG performance status.
- CT scan of the lung to determine soft tissue lesion details (e.g., size, lesion type, location, shape). [REDACTED]
- Obtain PFTs (spirometry, diffusion capacity (DLCO), lung volume tests, 6-minute walk or pulse oximetry, and FeNO tests).
- Laboratory tests, as follows:
 - a. Complete blood count (CBC with differentials).
 - b. Coagulation tests (APTT, INR, PT, PTA, PTT).
- Record the number of successful repeat ablations, if applicable.
- All AEs/SAEs.
- Record date of study completion.

8.2.6 Unscheduled Visits

The following data will be collected during each unscheduled visit:

[figure not shown]
- Reason for the unscheduled visit.
- AEs/SAEs, if applicable.
- Any update to concomitant medications and procedures.

9.0 DATA MANAGEMENT AND INTEGRITY

9.1 Data Completion and Record Keeping

Source Documents

Source documents are documents on which information regarding patients is first recorded, including printed, optical, or electronic documents. Investigator patient files or hospital records generally are the basis of source document information. This includes, but is not limited to, the following: original patient files; hospital/clinic records; original recordings/tracing; digital images from automated instruments (e.g., cameras); radiographs; device accountability records; photographic negatives; and, records kept at the investigation site, at the laboratories, and at other departments involved in the clinical investigation.

All cone beam CT scans (taken during the ablation procedure) and all conventional CT scans (taken during the post-ablation follow-up visits) should be sent in DICOM format (where possible) [redacted]

Source documents must be retained by the Investigator as part of the patient's permanent medical record. The information in the source documents is used to complete the eCRFs.

All information captured on the eCRFs should be completely and accurately supported in source documentation. Any additional information relevant to the study should be included in the source documents. Particularly, any deviations from the protocol or procedures should be recorded in the source documents. The Investigator will retain originals of all source documents, patient consent forms, and study data.

Electronic Data Capture

An EDC system will be used by site personnel to transfer data from source records (medical records and/or source document worksheets) onto common eCRFs. This system is a web-based, secure electronic software application (Medidata Rave, [name]; [contact]; [contact]; toll-free: [contact]). This system was designed and is developed and maintained by Medidata, Inc. in a manner that is compliant with national and international GCP data protection/data privacy and electronic record/electronic signature (e.g., 21 CFR Part 11) regulatory requirements. The EDC system will be used to facilitate the collection of all data at the site. Designated site personnel will be responsible for entering patient data into the EDC system. All external and Sponsor internal users will be trained on the EDC application at a level dependent on their planned function. An EDC digital User Manual will be available under the help menu within the Medidata Rave website to assist in the collection and entry of source data into the electronic casebook.

A 24/7/365 Help Desk Support line ([contact]; [contact]; toll free: [contact]; Email: [contact]) staffed by the outsourced vendor will also be available to respond to site and monitor questions.

Data Collection

Each EDC eCRF will be completed by the Principal Investigator (PI) or PI's designee. Every effort should be made to respond to all monitoring and/or data management questions on each eCRF as completion of the data is required by the protocol. A unique ID number will identify each patient. The patient's unique study ID number will be visible on each eCRF. At no time, should the patient name appear on the eCRFs.

All data should be recorded accurately and completely. The Investigator is responsible for reviewing and approving each completed eCRF. The Investigator will document assurance of overall review and approval by electronically signing each patient's electronic casebook.

Data Correction

Required data corrections to eCRFs will be prompted via automated electronic edit checks and/or queries manually created by Sponsor reviewers. The change, the person making the change, and the time the change was made to the eCRFs will be automatically captured in the audit trail within Medidata Rave.

Data Privacy

The collection, use, and disclosure of all personal data, including patient health and medical information, are to be maintained in compliance with applicable personal data protection and security laws and regulations that govern protected health information and the informed consent given by each patient. When collecting and processing such personal data, appropriate measures are to be taken to maintain the confidentiality of patient health and medical information and to prevent access by unauthorized persons.

None of the data collected and transmitted by Call Home Database is attributable to an identifiable patient.

Record Retention, Inspection, and Custody

The Investigator must maintain all documentation related to the study until notified by the Sponsor. The Investigator will allow representatives of the Sponsor, the FDA, or other government regulatory agencies to inspect all study records, eCRFs, and corresponding portions of the patient's office and/or hospital medical records at regular intervals during the study. These inspections are to verify adherence to the protocol, integrity of the data being captured on the eCRFs, and compliance with applicable regulations.

Study reports will not identify patients by name. These reports may be submitted to the FDA and/or regulatory authorities.

If custody of the clinical study records is transferred, notice of such a transfer should be given to the Sponsor no later than 10 working days after the transfer occurs.

9.2 Medical Dictionary Coding

Medical dictionary coding of medical history and verbatim AEs captured on eCRFs will be performed using a coding thesaurus algorithm. The Medical Dictionary for Regulatory Activities (MedDRA) will be used after data entry and query resolution, via auto-encoding and interactive coding processes.

9.3 Data Quality Assurance

A protocol deviation is any noncompliance with the study protocol, Good Clinical Practice, or protocol-specific requirements. A deviation (any activity conducted outside the parameters established by the study protocol) can be identified from a number of sources. Potential sources include, but are not limited to: a member of the Investigator's staff, a Sponsor representative during monitoring visits, or a member of the data management or statistical groups when entering or analyzing data. Regardless of the source, it is crucial to document the deviation in the protocol deviation eCRF. The Investigator will report protocol deviations to the IRB as required by the IRB procedures.

Steps to be taken to assure the accuracy and reliability of data include the selection of qualified investigators and appropriate sites, review of protocol procedures with the Investigator and associated personnel prior to the study, and periodic monitoring visits by the Sponsor. The Sponsor will review eCRFs for accuracy and completeness during on-site monitoring visits; any discrepancies will be resolved with the Investigator or designees, as appropriate.

Any deviations from the protocol or procedures should be recorded in the source documents.

All protocol amendments must be issued by the Sponsor, signed and dated by the Investigator, and should not be implemented without prior IRB approval, except where necessary to eliminate immediate hazards to the subjects or when the change(s) involve only logistical or administrative aspects of the study, e.g., change in monitor(s), change of telephone number(s). The Investigator reports the protocol amendments to the IRB/EC as per their local requirements.

Investigator Training

Prior to screening patients for this study, the PI, sub-Investigators, study coordinators, and other designated staff (as applicable) will be provided information on study execution,

data collection, and procedures specific to this clinical protocol.

Monitoring

This study will be monitored by the Sponsor to ensure the following:

- The rights and well-being of the patients are protected.
- The reported data is accurate, complete, and verifiable from source documents where utilized.
- The conduct of the study is in compliance with the currently approved protocol/amendment(s), applicable GCPs, and with applicable local/regional regulatory requirements.

The extent and nature of monitoring will be predetermined and agreed to by the Sponsor and investigators. Monitors will comply with established written standard operating procedures as well as procedures (i.e., monitoring plan) specified by the Sponsor for monitoring this study as characterized in the monitoring plan.

9.4 Protocol Deviations

Steps to be taken to assure the accuracy and reliability of data include the selection of qualified investigators and appropriate sites, the review of protocol procedures with the Investigator and associated personnel prior to the study, and periodic monitoring visits by the Sponsor. The Sponsor will review eCRFs for accuracy and completeness during on-site monitoring visits; any discrepancies will be resolved with the Investigator or designees, as appropriate.

10.0 STATISTICAL METHODS PLANNED IN THE PROTOCOL AND DETERMINATION OF SAMPLE SIZE

10.1 Statistical and Analytical Plans

The Sponsor Data Management and Biostatistics groups will be responsible for the analysis of data from this protocol. A comprehensive and detailed Statistical Analysis Plan will be finalized prior to database lock to supplement the statistical design and analysis described in this section.

Categorical variables will be summarized descriptively by frequencies and associated percentages. Continuous variables will be summarized descriptively by number of patients, mean, standard deviation, median, minimum, and maximum.

10.2 Study Design

This is a multicenter, single-arm study.

10.3 Treatment Assignment

This is a single-arm study where all enrolled patients will receive the same treatment: microwave ablation performed with the flexible probe using the NEUWAVE Flex Microwave Ablation System and Accessories. There will be no blinding or randomization.

10.4 Interval Windows

Interval windows are provided in Table 1: Schedule of Assessments. No additional windows are planned for analysis purposes.

10.5 Primary Endpoints

The primary objective of this study is to evaluate the NEUWAVE Flex Microwave Ablation System and Accessories in transbronchial ablation procedures for adult patients with medically inoperable primary soft tissue lesion that are ≤ 2 cm, located in the outer two-thirds of the lung and not closer than 1 cm to the pleura, at Visit 3, which is 30 days ± 7 days after the first ablation procedure, based on the following:

- a) Device user experience
- b) Technical success
- c) Technique efficacy.

The data for the evaluation of device user experience will come from the User Experience Survey, which will be completed by the treating physician following each ablation procedure throughout the study, when applicable.

Primary endpoints for technical success and technique efficacy are defined in Section 6.0, above.

The study will be descriptive in nature and thus no hypotheses for any of the primary endpoints are specified levels of significance.

10.6 Levels of Significance

No levels of significance are specified because no hypotheses are planned to be tested.

10.7 Analysis Sets

The primary analysis of safety and effectiveness endpoints will be performed on the Full Analysis Set, defined as all patients who are enrolled in the study and receive ablation through the flexible probe. A Per Protocol analysis set will be defined as all patients who had undergone the ablation procedure and have no major protocol deviations. Effectiveness analyses will be repeated for the Per Protocol Set.

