6.0 ENDPOINTS

6.1 Primary Endpoints

The primary endpoints include the following:

- Device user experience: The data will come from the User Experience Survey, which will be completed by the treating physician following each ablation procedure.
- Technical success, defined as: ablation of the target lesion according to the protocol and covered completely, with an adequate margin, as defined by the performing physician (that is, the ablation zone completely overlaps or encompasses the target lesion plus an ablative margin), as assessed by cone beam CT imaging, immediately following the procedure.
- Technique efficacy, defined as ablation of the target lesion according to the protocol and covered completely, with an adequate margin, as defined by the performing physician (that is, the ablation zone completely overlaps or encompasses the target lesion plus and ablative margin). Technique efficacy will be assessed using CT imaging at Visit 3, which is 30 days \pm 7 days after the first ablation procedure.

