7.0 INVESTIGATIONAL PLAN

7.1 Overall Study Design and Plan – Description

This is a multicenter, single-arm study for NEUWAVE Flex Microwave Ablation System in the ablation of soft tissue lesions of the lung for medically inoperable patients or those who elect not to have surgery. An experienced interventional pulmonologist or thoracic surgeon will determine whether a patient is “medically inoperable.” Indicators defining medically inoperable are, as follows: post-op predictive FEV1 < 40%; DLCO < 40%; hypoxemia or hypercapnia diabetes with end-organ damage; or, severe cerebral, cardiovascular, peripheral vascular disease, or chronic heart disease.

Prospective patients will be informed about the nature of the research, given the ICF to read, and if the patient understands the content, will be asked to provide consent by signing the ICF. Individuals scheduled for microwave ablation of the lung will be enrolled after providing informed consent and meeting study entry criteria. Patients will be followed for approximately 1 year following the first ablation procedure for safety and efficacy outcomes.

[REDACTED] Only participants who withdraw or are terminated prior to the planned intrabronchial flexible probe ablation procedure will be replaced.

[REDACTED]

[REDACTED]

[REDACTED]

The study will end when all patients have completed the 12-month, post-ablation follow-up period or have withdrawn early.

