7.2 Enrollment

A target total of approximately 40 patients, [REDACTED] will be enrolled across multiple study sites in the United States. A subject who signs the consent is considered screened and once treated they are considered enrolled into the study.

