7.6 Screening Failures

All patients signing consent who do not meet the inclusion and exclusion criteria or who do not have the ablation procedure initiated, will be recorded as screen failures. The relevant eCRF pages (demographics, reason for screen failure) will be completed for all screen failure patients and thereby the data will be included in the study database.

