7.7 Removal of Patients from the Study

In accordance with the current revision of the Declaration of Helsinki and the Code of Federal Regulations, a patient has the right to withdraw from the study at any time for any reason without prejudice to his/her future medical care by the physician or the institution. Should a patient (or patient's legally authorized guardian/representative) decide to withdraw from the study, all efforts will be made to collect all AEs they may have experienced. Patients who withdraw or are terminated prior to the ablation procedure will be replaced.

Participation may be terminated prior to completing the study for any of the reasons listed below (reasons that do not fit the categories below will be documented as "other").

Withdrawal of Consent:

If a patient chooses to withdraw early from the study, the eCRF completion page should be completed. When a patient's participation is terminated prior to completing the study, the reason for withdrawal is to be documented on the eCRF and in the source documentation.

Ablation:

The Investigator may withdraw a patient during the ablation procedure for any reason, including the following reasons:

1. Inability of Investigator to locate and target the soft tissue lesion.
2. Inability of patient to tolerate the anesthesia.

Death:

When available, the cause of death should be documented.

Lost to follow-up:

All patients should be encouraged to return for protocol required clinic visits for evaluation during the study follow-up period. If a patient is unable to return for a clinic visit or unable to be contacted by telephone, attempts to contact the patient should be documented in the source documents. Only after failing to contact the patient at the final follow-up visit, the patient will be considered lost to follow-up and the primary reason for early termination will be completed in the eCRF.

Site Termination or Study Termination:

The Sponsor may terminate a site or study at any time. When this occurs, all patients at the site will be withdrawn and documented as "early termination." Reasons for site or study termination may include, but are not limited to, the following:

- Administrative concerns (e.g., inadequate patient enrollment, investigator/institution non-compliance, change of business strategy, etc.).
- Safety issues, including those due to non-compliance, which substantially affect the risk-to-benefit ratio of the study patients at a site or for the study as a whole.

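### Technical success is estimated only among patients who received ablation, so a procedure stopped because the lesion could not be reached cannot lower the rate

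*Protocol*

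**What the plan says.** **Who is analysed.** Protocol 10.7 bases the primary safety and effectiveness analysis on the FAS, "defined as all patients who are enrolled in the study and receive ablation through the flexible probe". SAP 6 repeats this definition. Protocol 10.9 (Handling of Dropouts or Missing Data) and SAP 9.9 apply the same restriction to all analyses and summaries. SAP 6 then drops the Per Protocol set because enrolment stopped at 10, and SAP 9.10 rules out sensitivity analyses.

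**What is estimated.** Protocol 6.1 defines technical success as "ablation of the target lesion according to the protocol and covered completely, with an adequate margin, as defined by the performing physician", judged on cone beam CT straight after the procedure. SAP 9.4 reports the number and percentage with an exact 95% interval. The site assessment is in Table 6 and the independent reviewer's in Table 22, both on the FAS.

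**Which failure is foreseen.** Protocol 7.7 states: "The Investigator may withdraw a patient during the ablation procedure for any reason". The first reason listed is "Inability of Investigator to locate and target the soft tissue lesion".

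**How patients are classed.** Under Protocol 7.2, "once treated they are considered enrolled into the study". Under Protocol 7.6, consented patients "who do not have the ablation procedure initiated, will be recorded as screen failures". Protocol 7.1 says: "Only participants who withdraw or are terminated prior to the planned intrabronchial flexible probe ablation procedure will be replaced".

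**How the FAS is programmed.** A programming note under SAP Table 1 identifies FAS members by a non-missing ablation date on the Ablation Procedure CRF. Another note there uses the FAS as the denominator for every percentage in the table.

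**The concern.** Protocol 4.0 says that transbronchial ablation of lung lesions had not yet been reported in humans, and Protocol 10.8 gives the study's purposes as feasibility and sizing a later study. Getting the probe to the lesion through the airway is part of what has to be shown feasible. A patient in whom the procedure begins and the lesion cannot be located is a failure of the technique in any ordinary sense. On the FAS wording, that failure cannot count against the primary technical success rate.

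A later study that plans from patients taken to the procedure room needs success per started procedure. The planned rate gives success per delivered ablation. The two are equal only if every started procedure reached ablation, and no planned table shows whether that was so.

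**Working it through.** **Step 1. Follow one patient through the rules.** Take a patient whose procedure is begun, whose lesion cannot be located, and who receives no ablation.

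- Protocol 7.6: the procedure was initiated, so the patient is not a screen failure on that ground.
- Protocol 7.1 and 7.7: the patient did not leave before the procedure, so is not replaced.
- Protocol 7.2: the patient was not treated, so is not enrolled.
- Protocol 10.7 and SAP 6: no ablation was received, so the patient is outside the FAS.
- Protocol 6.1: the lesion was not ablated and covered, so technical success was not achieved.

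The patient fails the endpoint and is outside its denominator. The visible text gives no single class for this patient. Redacted text in the procedure sections and the Schedule of Assessments footnotes may define when the procedure starts.

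**Step 2. Look for another denominator.** There is no Per Protocol set (which would also require ablation) and no sensitivity analysis, so none is summarized. Table 1 shows the number consented and the number in the FAS, but does not separate screen failures from procedures started and stopped. Under its own note, the percentage in the FAS row is FAS/FAS = 100% whatever happened.

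**Step 3. Size.** The plan states no rate to reproduce. Ten subjects received ablation (SAP 7). The number of successes among them, S, and the number of started procedures without ablation, k, are not given. Both are assumptions here.

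- FAS rate: S/10. Rate per started procedure: S/(10 + k).
- Difference: S/10 − S/(10 + k) = S·k / [10(10 + k)]. For S = 10, k = 1: 10/110 = 9.1 points. For S = 10, k = 2: 20/120 = 16.7 points.
- Exact (Clopper-Pearson) limits for x out of n: lower = 0.025 quantile of Beta(x, n − x + 1); upper = 0.975 quantile of Beta(x + 1, n − x), or 1 when x = n. For 10/10 the lower limit is 0.025^(1/10) = 69.2%.

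| S | k = 0 (FAS rate) | k = 1 | k = 2 |
|---|---|---|---|
| 10 | 100% (69.2–100) | 90.9% (58.7–99.8) | 83.3% (51.6–97.9) |
| 9 | 90.0% (55.5–99.7) | 81.8% (48.2–97.7) | 75.0% (42.8–94.5) |
| 8 | 80.0% (44.4–97.5) | 72.7% (39.0–94.0) | 66.7% (34.9–90.1) |
| 7 | 70.0% (34.8–93.3) | 63.6% (30.8–89.1) | 58.3% (27.7–84.8) |

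Over this range, one excluded failure is worth 6.4 to 9.1 points on the rate and 4.0 to 10.4 points on the lower limit (differences taken before rounding). Two are worth 11.7 to 16.7 and 7.1 to 17.6 points. With k = 0 nothing changes.

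**Step 4. Compare the two statements of FAS membership.** SAP 6 requires ablation received; the Table 1 note requires a recorded ablation date. If the date is left blank when nothing is ablated, they select the same subjects. If a site dates one stopped case in addition to the 10 ablated, the date rule gives an FAS of 11 and SAP 6 gives 10. The CRF and its completion instructions are not in the documents, so which applies cannot be determined.

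**The case against.** **The conditional rate is a legitimate choice.** The study is descriptive and tests no hypotheses, and technical success is worded as a result of ablation judged on an image taken afterwards. Untreated patients are not enrolled, so their exclusion is consistent with Protocol 7.2. This stands. The planned rate is not wrong for what it estimates, and the point is that a second quantity, closer to the stated purpose, is missing.

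**The listings already expose such cases.** SAP 9.1 lists all CRF data for all subjects, and Listings 22 and 32 cover ablation procedures and completion or discontinuation. A reader could look there, but a listing does not change the summary rate or its interval.

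**The size is assumed.** This stands in full. No success count, access-failure count or access-failure rate is given. SAP 7 reports 10 ablated subjects and says nothing about procedures started and abandoned.

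Three stronger readings are tempting, and the documents do not support them:

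- *That the reported rate is inflated.* This needs at least one started procedure without ablation, and no passage reports one.
- *That the SAP contradicts itself on FAS membership.* The ordinary reading of the programming note is that without an ablation there is no ablation date, and then it agrees with SAP 6. A mismatch is possible but not shown.
- *That the observed-data rule in Protocol 10.9 would drop a blank technical success entry from the rate.* Table 6 shows the percentage under a single N header and lacks the note, found under Tables 5, 10 and 11, that observed responses are summarized. The shell points to the full FAS as denominator.

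**Conclusion.** The concern holds in a limited form. As written, the technical success rate is conditional on ablation being delivered. A failure that Protocol 7.7 itself foresees cannot lower it, and no other denominator is summarized. The rate is valid as success given ablation, and overstates success per started procedure only if such a failure occurred. If all 10 ablated subjects succeeded, one such patient would move 100% to 90.9% and two would move it to 83.3%. If there were none, the two rates coincide, and the report would gain only a stated zero.

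This rests on the visible definitions and on assumed counts. Redacted text could supply a start point for the procedure or a class for these patients. It is worth fixing because the remedy is cheap and serves the study's stated purpose, not because an error in the results has been shown.

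**What to change.** 1. Keep the FAS technical success rate and label it *conditional on ablation* in Tables 6 and 22.
2. In Table 6, add a supportive rate with exact 95% interval over all started procedures, counting failure to locate, target or ablate the lesion as No. Use the protocol's own start point if the redacted text gives one; otherwise state the one used. If started procedures cannot be identified from the ablation-procedure and completion/discontinuation records, say so in the report.
3. In Table 1, add a row *procedure started, not ablated*, with reasons and a zero if there were none. Base the percentage in the FAS row on consented subjects.
4. Align the ablation-date programming note with SAP 6, so that a date recorded for a procedure without ablation does not by itself confer FAS membership.

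The cost is a few lines of SAP wording and minor programming, with no new data collection planned. The supportive rate may be less favourable than the FAS rate. If the protocol gives no start point, one has to be chosen after enrolment has closed, and the report should disclose that.
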